### 2.6.3 Known and Potential Risks

Inhibition of MTP is expected to cause accumulation of triglycerides in intestinal mucosa and hepatocytes, and malabsorption of fat and fat-soluble vitamins from the diet. Major histological findings from non-clinical toxicological experiments showed increased incidences of lipid vacuolation in small intestinal mucosal epithelium and hepatocytes.

However, increased incidences of liver and small intestine tumours in mice were not noted in clinical studies and may not be expected to occur in clinical use due to the lack of genotoxicity, immunotoxicity, or other cellular injury associated with high levels of lomitapide exposure. In addition, unphysiological factors in the non-clinical experiments such as vitamin E depletion and severe hypocholesterolaemia will be prevented by administering dietary supplements (see Section 6.3 *Dietary Supplements*) and by closely monitoring LDL-C levels (see Section 1.2 *Flow Chart of Study and Follow-up*).

In the pivotal phase III study, 10 of 29 patients experienced elevations of ALT and/or AST  $>3 \times$  ULN once or more during the study. Four of these patients exhibited ALT increases  $>5 \times$  ULN. No patient discontinued treatment permanently due to LFT elevations and all elevations were managed either by dose reduction or temporary interruption of lomitapide as per protocol. Of note, 3 of 4 patients with LFT elevations  $>5 \times$  ULN reported consuming quantities of alcohol higher than those allowed per protocol. No patient experienced elevations in bilirubin or AP levels (Cuchel, Meagher et al. 2013).

During the extension study, 4 of 19 (21.1%) patients experienced a  $\geq 5 \times$  ULN increase in ALT or AST. Increases  $\geq 5 \times$  ULN were typically associated with concomitant use of CYP 3A4 inhibitors or excess alcohol use. These events were successfully managed by discontinuing offending medication, lomitapide dose reductions or suspension, and reintroduction of lomitapide after normalisation of transaminases (Blom, Averna et al. 2017).

Management of elevated hepatic aminotransferases in this study is carefully specified by an algorithm in Section 7.3.2 *Dose Modification, Interruption or Discontinuation for Adverse Events*. In addition, an independent DSMB will provide oversight of patient safety (see Section 4.3 *Data Safety Monitoring Board*).

Due to the potential for lomitapide to cause elevations in ALT/AST levels, it should be used in caution in patients who consume alcohol. Further, caution should be exercised when lomitapide is co-administered with agents known to be hepatotoxic (see Section 7.6.3 *Non-Permitted Concomitant Medication, Food or Substances*) and is contraindicated in patients with moderate to severe hepatic impairment and those with active liver disease, including patients with unexplained persistent abnormal liver function tests (see Section 5.2 *Exclusion Criteria*).

In the pivotal phase III study, hepatic fat was measured non-invasively using NMR. Mean hepatic fat content of 20 evaluable patients was 1.0% at Baseline, 8.6% at Week 26, 5.8% at Week 56 and 8.3% at Week 78 (Cuchel, Meagher et al. 2013). In the extension study, 18 patients had  $\geq 1$  assessment of hepatic fat by NMR after Baseline. Median hepatic fat increased from 0.7% at Baseline to 6.5% at Week 78 and was 7.7%, 10.3%, and 10.2% at Weeks 126, 174, and 246, respectively (Blom, Averna et al. 2017).

Clinical data suggest that hepatic fat accumulation is reversible after stopping treatment with lomitapide. For this reason, hepatic fat content will be measured 4 weeks after EoT in patients who opt not to participate in or are unsuitable for the Expanded Access Programme (EAP;

<18 years of age)/opt not to transition to commercial product (≥18 years of age; see Section 8.1.2 *Safety Assessments*).

The most common AEs in the phase III study included abdominal pain or discomfort, nausea, vomiting, dyspepsia, diarrhoea, and constipation. Diarrhoea was the most common symptom. This finding is expected since MTP inhibition is known to cause fat malabsorption and steatorrhoea. As the occurrence and severity of GI AEs associated with the use of lomitapide decreases in the presence of a low-fat diet, patients will start to follow a diet supplying <20% of energy from fat or <30 g fat, whichever is the lesser amount at the Start of the Run-in Period, and will continue this diet until the EoT or through the administration of lomitapide in the EAP (<18 years of age) or during administration of commercial lomitapide (≥18 years of age; see Section 8.6.1 *Diet Instructions and Diet Records*).

In the pivotal phase III study, decreased body weight was reported as an AE in 6 of 29 patients. All cases were assessed as mild to moderate in severity, non-serious and none led to study drug discontinuation. The combination of gastrointestinal (GI) symptoms (e.g., diarrhoea, nausea), fat malabsorption, and adherence to a strict fat-restricted diet, may result in a calorie deficit relative to daily requirements. Appropriate dietary supervision and monitoring is an important component to improve GI tolerability and the maintenance of an adequate diet to avoid unintended weight loss. In this study, weight will be measured at each visit after the Run-in Period and patients of normal or below normal body weight based on gender and age-specific World Health Organization (WHO) growth charts with weight loss >3% since the last visit will be instructed by the dietitian on how to increase caloric intake based on individual needs (see Section 8.6.1 *Diet Instructions and Diet Records*). Patients with below normal body weight any time during the study who continue to lose weight while on study medication despite all appropriate measures taken to correct for the weight loss and who are deemed to be at clinical risk in the judgment of the treating investigator should discontinue study medication and should be followed until an acceptable stable weight is reached as judged by the investigator (see Section 7.3.2 *Dose Modification, Interruption or Discontinuation for Adverse Events*).

MTP inhibition with lomitapide is likely to cause a deficiency in fat-soluble vitamins, particularly vitamin E. Therefore, all patients in this study will receive daily oral supplementation with vitamin E (200 IU for patients 5 to 8 years of age, 400 IU for patients 9 to ≤17 years of age) and an EFA supplement containing approximately 200 mg linoleic acid, 210 mg ALA, 110 mg EPA, and 80 mg DHA (see Section 6.3 *Dietary Supplements*).

The SPC (included in the Lojuxta® SPC in lieu of an Investigator's Brochure [IB]; see Section 18.1 *Source Documents*) provides guidance in key areas to minimise risk to patients during treatment with lomitapide, which is reflected in the design of this study. Use of lomitapide in patients with moderate or severe hepatic impairment, active liver disease, or pregnancy is contraindicated (see Section 5.2 *Exclusion Criteria*). Contraindications also include co-administration with strong or moderate inhibitors of CYP 3A4 and co-administration with doses of simvastatin >40 mg (see Section 7.6.3 *Non-Permitted Concomitant Medication, Food or Substances*). In the presence of atorvastatin (a weak CYP 3A4 inhibitor), lomitapide should be taken 12 hours apart. Since patients will be required to remain on their concomitant LLT (including LA when applicable) established during the 6-week Run-in Period during the Efficacy Phase of the study through Week 24±3 days, a potential concomitant treatment with atorvastatin will remain unchanged during the Efficacy Phase, when lomitapide dosing will start. If atorvastatin is given concomitantly, it should be administered in the morning to separate it from lomitapide dosing by 12 hours. If during the 80-week Safety Phase it is not possible to administer atorvastatin and lomitapide 12 hours apart, the lomitapide dose should be reduced by half. After a minimum period of 4 weeks following dose reduction the patient can be re-challenged with a higher dose of lomitapide once these issues resolve (i.e., if atorvastatin can be administered 12 hours apart or if atorvastatin is discontinued), but the dose during the Safety Phase cannot exceed the MTD established during the Efficacy Phase unless eligibility for exceptional dose escalation is met (described in Section 7.3.1 *Dose Escalation, Dose*

*Reduction and Re-challenge*). For patients on a stable maintenance dose of lomitapide who receive any other weak CYP 3A4 inhibitor, the dose of the medications should be separated by 12 hours (see Section 7.3.3 *Dose Modification for Concomitant Medication*). Use in patients with known significant or chronic bowel disease is also contraindicated since MTP inhibition is known to cause fat malabsorption and steatorrhea. Use in patients with rare hereditary problems of galactose intolerance, the Lapp-lactase deficiency or glucose-galactose malabsorption, are contraindicated in accordance with EU guidance (EC Volume 3B Guidelines, *Medicinal Products for Human Use, Safety, Environment and Information: Excipients in the Label and Package Leaflet of Medicinal Products for Human Use*, July 2003) since the drug product contains lactose (see Section 5.2 *Exclusion Criteria*). Hepatic aminotransferase levels must be determined prior to initiating therapy, and then monitored prior to each dose escalation, and regularly during treatment (see Section 1.2 *Flow Chart of Study and Follow-up*). In the event that hepatic aminotransferases become elevated, a detailed algorithm for dose adjustment or treatment discontinuation is provided (see Section 7.3.2 *Dose Modification, Interruption or Discontinuation for Adverse Events*). This algorithm is based on the approach agreed with the DSMB hepatologist that was used successfully in the pivotal phase III study and is consistent with the FDA's draft guidance *Drug-Induced Liver Injury: Premarketing Clinical Evaluation*, October 2007. Dietary advice, including fat content (see Section 8.6.1 *Diet Instructions and Diet Records*) and supplementation with vitamin E and essential fatty acids (see Section 6.3 *Dietary Supplements*), is also specified, and dosing is escalated gradually to minimise GI side effects and allow for regular hepatic aminotransferase determination (see Section 7.2 *Treatment Schedule*). These elements of safety monitoring are designed to allow the optimum individualised dose to be selected for each patient in order to maximise the benefit of LDL-C reduction, ensure compliance with treatment, and avoid AEs.

#### **2.6.4 Benefits and Risks Conclusions**

Patients with HoFH deal with a life-threatening disease every day in the absence of effective treatment to reduce their LDL-C to target levels. For the first time, it is now feasible to reach target LDL-C goals and maintain these levels during chronic treatment. LDL-C lowering of lomitapide was modelled to increase median life expectancy of HoFH patients by 11.6 years and delay time to the first MACE by 5.7 years (Leipold, Raal et al. 2017).

Lomitapide treatment is a major advance in the treatment of a devastating disease through modification of a risk factor that is currently uncontrolled by available treatment interventions, supporting a favourable benefit-risk assessment for its use in this high-risk patient population.

In this study, lomitapide will be carefully titrated to the MTD based upon safety, tolerability and LDL-C levels and safety will be monitored by an independent DSMB (see Section 4.3 *Data Safety Monitoring Board*). Therefore, the benefits will outweigh the risks.

### **2.7 Rationale of the Study and of the Study Design**

Lomitapide has been approved for use in adult patients with HoFH in the European Union (EU) and European Economic Area (EEA), United States of America (USA), Israel, Argentina, Canada, Colombia, and Japan. This study is designed to determine if lomitapide is effective and can be safely administered to paediatric patients with HoFH. If the efficacy and safety so far observed in adults is confirmed in paediatric patients, the potential exists to significantly lower LDL-C levels in paediatric patients with HoFH. Furthermore, the lower LDL-C levels may reduce atherosclerosis progression and would be expected to benefit these paediatric patients with HoFH.

A single-arm, non-comparator design has been selected due to the rarity of the disease and because the evaluation of safety variables such as growth and sexual maturation requires longer term observation than would not be feasible in the context of a placebo-controlled study.

In addition, similar efficacy cannot reasonably be assumed in a 2-arm design with standard of care LLT including LA as comparator, and, as a result, randomisation of these very high risk patients to placebo for longer than 6 months would not be acceptable.

Finally, the high incidence of GI AEs expected in lomitapide-treated patients and the corresponding inability to keep patients and physicians blinded to treatment would introduce an assessment bias.

To mitigate the disadvantages of a single-arm design, the study includes a Run-in Period of at least 6 weeks during which current LLT (including LA, when applicable) will be stabilised to establish Baseline levels allowing each patient to serve as his/her own control. Patients will also remain on stable LLT (including LA, when applicable) during the Efficacy Phase of the study through Week 24±3 days.

## **3 STUDY OBJECTIVES**

### **3.1 Primary Objective**

Evaluate the efficacy of lomitapide as defined by the percent change in LDL-C at the MTD at Week 24±3 days compared to Baseline when added to stable LLT (including LA when applicable) in paediatric patients (5 to ≤17 years of age) with HoFH.

### **3.2 Secondary Objectives**

- Evaluate the efficacy of lomitapide in paediatric HoFH patients as assessed by:
  - Percent change from Baseline at Week 24±3 days in lipid parameters, including total cholesterol (TC), non high-density lipoprotein cholesterol (Non-HDL-C), very low-density lipoprotein cholesterol (VLDL-C), triglycerides (TG), lipoprotein(a) [Lp(a)], and apolipoprotein B (apo B).
  - Percent change from Baseline in TC, non-HDL-C, LDL-C, TG, VLDL-C, Lp(a), and apo B at all other time-points through Week 104±1 week.
  - Change in LLT and LA from Week 24±3 days through Week 104±1 week.
  - Number (percent) of patients achieving the EAS recommended target LDL-C of <135 mg/dL (3.5 mmol/L) at Week 24±3 days and at any time on study.

### **3.3 Safety Objectives**

- Evaluate the long-term safety and tolerability of lomitapide in paediatric HoFH patients as assessed by:
  - Incidence in reported AEs and in clinically significant abnormal findings of physical examinations including weight and BMI, electrocardiogram (ECG), standard of care echocardiography (if available), vital signs, pulmonary function tests (PFT), and laboratory parameters including hepatic and renal function tests.
  - Effects on growth, bone health and bone age will be assessed using both measurements of children's height and growth charts to track age-appropriate progress at Screening and from Baseline at every visit through Week 104±1 week and/or at EoT, together with analysis of Vitamin D and K levels at Screening, Baseline, Week 24±3 days, Week 56±3 days, Week 80±1 week, Week 104±1 week and/or at EoT (and at Week 108 for patients who opt not to participate in or are unsuitable for the EAP [<18 years of age]/opt not to transition to commercial product [≥18 years of age]).
  - Potential effects on maturation, reproductive development, gonadotropins, and variables of the pituitary-adrenal axis at Screening, Baseline, Week 56±3 days, Week 104±1 week

and/or at EoT will be analysed; potential effects on the levels of sex steroids will be analysed for patients assessed as Tanner Stage  $\geq 2$ .

- Lipid accumulation in the liver as measured by nuclear magnetic resonance (NMR) imaging or echography (i.e., ultrasound scan) at Baseline and at Week  $24\pm 3$  days, Week  $56\pm 3$  days, and at Week  $104\pm 1$  week (for patients who opt not to participate in or are unsuitable for the EAP [ $<18$  years of age]/opt not to transition to commercial product [ $\geq 18$  years of age], lipid accumulation in the liver will be measured at Baseline, at Week  $24\pm 3$  days, Week  $56\pm 3$  days, and at Week 108). All patients will undergo NMR imaging unless it is contraindicated or not feasible (e.g., due to the need for sedation or general anaesthesia in very young or anxious patients). In this case, ultrasound scans will be used at the discretion of the investigator.

### **3.4 Exploratory Objectives**

- Evaluate exploratory assessments of:
  - Change from Baseline at Week  $56\pm 3$  days and Week  $104\pm 1$  week in mean carotid intima-media thickness (CIMT, mandatory) and flow-mediated dilatation (FMD, whenever possible).
  - The resolution and/or regression of pre-existing xanthomas at Week  $56\pm 3$  days and at Week  $104\pm 1$  week.
  - Changes from Baseline through Week  $24\pm 3$  days in cholesterol and triglyceride content of VLDL, intermediate density lipoprotein (IDL), LDL and HDL, particle number and size of VLDL, LDL, and HDL as well as particle number of their respective lipoprotein subclasses (large, medium, and small) as assessed based on 2D NMR (Liposcale® Test) of pharmacokinetics (PK) samples.

### **3.5 Palatability Objective**

- Assess the palatability of the study medication using a 5-point facial hedonic scale anchored with descriptors, to record the children's assessment of palatability in terms of overall liking.
- The parent(s)/legal guardian(s) interpretation of the child's reaction/facial expression will be used to determine whether they find lomitapide "pleasant", "unpleasant" or are "not sure".
- Ease of administration of the study medication and dietary supplements by the parent(s)/legal guardian(s) will be assessed using the following question at each visit during the treatment phase: "Do you sometimes have problems in giving the medication to your child because he/she refuses to take it or throws it up immediately after taking it? (Yes/No)."

### **3.6 Pharmacokinetic Objective**

- Evaluate the PK of lomitapide in paediatric HoFH patients through sparse blood sampling.

## 4 INVESTIGATIONAL PLAN

All references to “the investigator” throughout this document refer to “the investigator or a delegated sub-investigator”.

### 4.1 Study Endpoints

#### 4.1.1 *Primary Endpoint*

- Percent change from Baseline in LDL-C at Week 24±3 days.

#### 4.1.2 *Secondary Endpoints*

- Percent change from Baseline at Week 24±3 days for the following lipid parameters: TC, Non-HDL-C, VLDL-C, TG, Lp(a), and apo B.
- Percent change from Baseline at all other time points through Week 104±1 week for the following lipid parameters: LDL-C, TC, Non-HDL-C, VLDL-C, TG, Lp(a), and apo B.
- Total number and percent of patients with a change from Baseline in LLT and LA from Week 24±3 days through Week 104±1 week.
- Total number and percent of patients achieving the EAS recommended target LDL-C of <135 mg/dL (3.5 mmol/L) in paediatric HoFH patients at Week 24±3 days and at any time on study.

#### 4.1.3 *Safety Endpoints*

- Incidence of AEs overall and by severity, and relatedness.
- Physical examinations including regular measurements of height, weight, and BMI.
- Sexual maturation (Tanner staging).
  - In patients with Tanner Stage ≥2: Change from Baseline in sex hormones (serum testosterone and serum oestradiol).
- 12-Lead safety ECG (read locally), standard of care echocardiography (if available), vital signs and blood pressure.
- PFT.
- Laboratory tests:
  - Standard haematology (complete blood count [CBC]) and clinical chemistry panels).
  - Liver function tests: ALT, AST, gamma-glutamyl transferase (GGT), alkaline phosphatase (AP), total bilirubin, and serum albumin.
  - High-density lipoprotein cholesterol (HDL-C) and apolipoprotein A-I (apo A-I).
  - Creatinine kinase (CK).
  - Serum lipase.
  - Serum levels of essential fatty acids (EFA): Linoleic acid, alpha linoleic acid (ALA), eicosapentaenoic acid (EPA), docosahexaenoic acid (DHA), arachidonic acid (AA), and eicosatrienoic acid.
  - Serum concentrations of fat-soluble vitamins: Vitamin A (retinol), vitamin E (alpha tocopherol), ratio of vitamin E to total lipids (total cholesterol plus fasting triglycerides), and vitamin D (25-hydroxy-D). Levels of vitamin K will be assessed indirectly by measuring total and uncarboxylated levels of serum osteocalcin. (Bone health will be

assessed indirectly using growth to track age-appropriate progress, and measurement of 25-hydroxy-D as well as total and uncarboxylated osteocalcin levels.)

- Pituitary-adrenal hormone levels (thyroid stimulating hormone [TSH], follicle stimulating hormone [FSH], luteinising hormone [LH], adrenocorticotrophic hormone [ACTH], and morning serum cortisol).
- Urinalysis.
- Lipid accumulation in the liver as measured by NMR imaging or echography (i.e., ultrasound scan) at Baseline and at Week 24±3 days, Week 56±3 days, and at Week 104±1 week (for patients who opt not to participate in or are unsuitable for the EAP (<18 years of age)/opt not to transition to commercial product (≥18 years of age), lipid accumulation in the liver will be measured at Baseline and at Week 24±3 days, Week 56±3 days, and at Week 108). All patients will undergo NMR imaging unless it is contraindicated or not feasible (e.g., due to the need for sedation or general anaesthesia in very young or anxious patients). In this case, ultrasound scans will be used at the discretion of the investigator.

#### **4.1.4      *Exploratory Endpoints***

- Percent change from Baseline at Week 56±3 days and Week 104±1 week in CIMT and FMD.
- Total number and percent of patients with resolution and/or regression of pre-existing xanthomas at Week 56±3 days and at Week 104±1 week.
- Changes from Baseline through Week 24±3 days in cholesterol and triglyceride content of VLDL, IDL, LDL and HDL, particle number and size of VLDL, LDL, and HDL as well as particle number of their respective lipoprotein subclasses (large, medium, and small) as assessed based on 2D NMR (Liposcale® Test) of PK samples at Week 4±3 days, Week 8±3 days, Week 12±3 days, Week 16±3 days, Week 20±3 days and at Week 24±3 days.

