***Exploratory objectives***

To evaluate the exploratory assessments of:

- Change from Baseline at Week 56±3 days and Week 104±1 week in mean carotid intima-media thickness (CIMT, mandatory) and flow-mediated dilatation (FMD, whenever possible).
- Resolution and/or regression of pre-existing xanthomas at Week 56±3 days and at Week 104±1 week.
- Changes from Baseline through Week 24±3 days in cholesterol and triglyceride content of VLDL, intermediate density lipoprotein (IDL), LDL and HDL, particle number and size of VLDL, LDL, and HDL as well as particle number of their respective lipoprotein subclasses (large, medium, and small) as assessed based on 2D NMR (Liposcale® Test) of pharmacokinetics (PK) samples.

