### **8.4.2      *Assessment of Carotid Intima-Media Thickness and Flow-mediated Dilation***

Carotid intima-media thickness (CIMT, mandatory) and flow-mediated dilation (FMD, whenever possible) will be assessed using ultrasound scan to evaluate carotid atherosclerotic vascular disease and brachial artery dilation after a transient period of forearm ischaemia at Baseline (Visit 4, D0), at Visit 18 (Week 56±3 days), and at EoT (Week 104±1 week).

[figure not shown]

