#### **12.1.1 Tests of Hypotheses and Significance Levels**

The primary and secondary efficacy parameters collected during the Efficacy Phase of the study will be statistically tested using a 2-sided test at the 5% significance level.

To address the efficacy objectives, the efficacy parameters will be tested sequentially in a step-wise fashion, thereby controlling the overall type I error. First, the primary testing for percent change from Baseline in LDL-C at Week 24±3 days will be performed. If this test is statistically significant with a 2-sided  $\alpha = 0.05$  and is statistically significant in a positive

direction, then the tests of the secondary hypotheses will be performed in the following specified order at Week 24±3 days:

1. Non-HDL-C
2. TC

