### **12.1.2 Determination of Sample Size**

At least 30 evaluable patients (≥8 patients in each of the following age groups, determined by age at Baseline: 5 to 10 years, 11 to 15 years, and 16 to ≤17 years) are required at Week 24±3 days to provide 92% power, assuming a 25% reduction from Baseline in LDL-C with a standard deviation (SD) of 40% and a 2-sided  $\alpha$  of 0.05. To allow for up to 33% dropout during the Efficacy Phase (prior to Week 24±3 days), an additional 15 patients will be enrolled, resulting in a total sample size of approximately 45 patients. Enrolment will be stratified to ensure approximately equal numbers of patients in the following age groups: 5 to 10 years, 11 to 15 years, and 16 to ≤17 years.

As a conservative assumption, the estimated 25% mean reduction represents approximately 60% of the 41% mean reduction from Baseline to Week 26/End of Efficacy Phase seen in the adult study UP1002/733-005, Intent-to-Treat (ITT) Population. This is the same assumption that was used for the sample size in the adult study. The SD represents an approximate 1/3 increase from the 31% SD observed in the adult study. This increase in SD was used to account for potentially increased variability across the 3 age groups.

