#### **12.3.7 *Planned Analysis for Exploratory Endpoints***

The percentage change from Baseline in mean CIMT and mean FMD at Week 56±3 days and at Week 104±1 week will be assessed overall and by age group.

The number and percentage of patients with (tendon/cutaneous) xanthomas present, and locations, will be summarised overall and by age group at Baseline, Week 56±3 days and Week 104±1 week. The number and percentage of patients with resolution and regression of pre-existing xanthoma (Baseline) to Week 56±3 days and Week 104±1 week will be summarised overall and by age group.

Changes from Baseline in parameters assessed by the Liposcale® Test will be summarised at Week 4±3 days, Week 8±3 days, Week 12±3 days, Week 16±3 days, Week 20±3 days and at Week 24±3 days.

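### FMD is fixed as percent change from Baseline like CIMT, but a dilation can lie near or below zero, so its mean percent change can drift upward with no true effect; absolute change would not

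*Protocol*

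**What the plan says.** The exploratory endpoint in Section 4.1.4, repeated in the synopsis (Section 1.1), is "Percent change from Baseline at Week 56±3 days and Week 104±1 week in CIMT and FMD". The planned analysis in Section 12.3.7 follows it, both for all children together and within each age band: "The percentage change from Baseline in mean CIMT and mean FMD at Week 56±3 days and at Week 104±1 week will be assessed".

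The objective is worded more loosely. The synopsis has "Change from Baseline at Week 56±3 days and Week 104±1 week in mean carotid intima-media thickness", with FMD in the same sentence, and Section 3.4 says the same. Neither uses the word percent.

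Section 8.4.2 describes FMD as an ultrasound measurement of "brachial artery dilation after a transient period of forearm ischaemia", taken at Baseline, Week 56 and Week 104. CIMT is mandatory; FMD is done whenever possible. The protocol gives no unit or formula for FMD, no expected baseline, no measurement error and no rule for baselines at or below zero. No hypothesis test is attached to FMD.

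**The concern.** Percent change divides by the baseline value. For CIMT the divisor is a thickness well above zero. For FMD it is itself a difference between two vessel diameters, so it can be small, zero or negative through disease or measurement error. This holds whether dilation is recorded in millimetres or in percent.

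Two things follow:

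- The scale gives equal changes very different scores. If FMD is in percent dilation, a child going from 1 to 4 scores 100 × 3/1 = +300%, and a child going from 8 to 11 scores 100 × 3/8 = +38%. A baseline of zero has no score, and a negative baseline reverses the sign.
- Error in the baseline does not cancel. A baseline that is too low by chance inflates the ratio more than one that is too high deflates it, so the average moves upward even when nothing has changed.

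For a dilation response, upward reads as improvement. The study has no control arm (Section 2.7) in which the same drift would show.

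**Working it through.** **The plan's own figure.** The protocol states no figure for FMD. Its only sample-size figure concerns LDL-C: 30 evaluable patients "to provide 92% power, assuming a 25% reduction from Baseline in LDL-C with a standard deviation (SD) of 40"%. Check: 25/(40/√30) = 3.423, and 3.423 − 1.960 = 1.463, which gives 92.8% by the normal approximation; the noncentral t gives 91.1%. The stated 92% is reproduced. Only the 30 is used below, as a convenient trial size; it is a Week 24 LDL-C number, not an FMD number.

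**Inputs assumed, not in the protocol.** FMD in percent dilation; mean 4, 6 or 8; between-child SD 2 or 3; measurement SD per visit 1, 1.5 or 2.5. This gives 18 combinations.

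**Model with no true change.** Baseline b = T + e₁ and follow-up f = T + e₂, with the same true value T and independent errors. Per-patient percent change is 100 × (f − b)/b. For one child the leading term of its expectation is 100 × s²/T², where s is the measurement SD. It is always positive and grows quickly as T falls:

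- T = 8, s = 1: 100 × 1/64 = +1.6%
- T = 4, s = 2.5: 100 × 6.25/16 = +39%; at this ratio the approximation is rough, so simulation is needed
- CIMT, assuming T = 0.5 mm and s = 0.02 or 0.04 mm: 100 × 0.0004/0.25 = +0.16% and 100 × 0.0016/0.25 = +0.64%; simulation gives +0.2% and +0.7%

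**Simulation.** One million children per combination, grouped into trials of 30. True values were floored at 0.5, and baselines of 0.1 or less were dropped from the percent-change calculation; both steps make the result milder. Selected rows:

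| Mean | Between-child SD | Measurement SD | Median trial mean % change | Trials with mean above 0 | Share of sum of squares from the 3 lowest baselines | Baselines ≤ 0 |
|---|---|---|---|---|---|---|
| 8 | 2 | 1 | +2.0% | 69% | 30% | 0.0% |
| 8 | 3 | 1.5 | +5.4% | 75% | 51% | 0.7% |
| 6 | 3 | 1.5 | +9.0% | 75% | 65% | 2.8% |
| 6 | 2 | 2.5 | +25.3% | 88% | 71% | 3.0% |
| 4 | 3 | 1 | +6.2% | 65% | 68% | 5.3% |
| 4 | 2 | 2.5 | +31.5% | 81% | 75% | 10.1% |

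Across all 18 combinations:

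- The median trial mean is positive every time, from +2.0% to +31.5%.
- Between 65% and 88% of null trials have a mean above zero, against 50% expected.
- The three lowest-baseline children of 30 carry more than half of the sum of squared percent changes in 14 combinations and less than half in 4.
- Absolute change averages 0.00 every time and is above zero in 49% to 50% of trials.
- The ratio of group means stays within ±0.1% of no change.

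**By age group.** Section 12.3.7 also reports by age group, where Section 12.1.2 asks for at least 8 evaluable patients each. At mean 6, between-child SD 2.5 and measurement SD 2, with baselines above 0.5 kept, the 5th to 95th percentile range of the null mean percent change is about −11% to +44% for 30 children and −28% to +76% for 8.

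**The case against.** **The premise is partly external.** The protocol does not say that FMD is a percentage or that these children's baselines are near zero. This stands: every size above is conditional. In the most favourable combination the drift is about +2%, and the lowest baselines do not always dominate. What does not depend on the unit is that a dilation is a difference and can be near zero.

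**Section 12.3.7 can be read as change in the group mean**, which does not drift. That reading is possible. The endpoint in Section 4.1.4 favours a per-patient calculation, and the objective uses mean CIMT as the name of the measure. Two readings with different bias are themselves a reason to clarify.

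**The bias belongs to one summary statistic.** The median individual percent change has no upward drift. With all baselines kept it lies between 0% and −17% across the grid. It is therefore no clean substitute where baselines are low.

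**Details can go in the statistical analysis plan.** Summary statistics can. The percent scale, however, is already fixed in the protocol's endpoint.

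Two stronger readings are tempting and are not supported:

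- *The objective and endpoint contradict each other.* Percent change is one way to express change, and the same objective sentence covers CIMT, for which percent change is acceptable. The objective simply leaves room for the better scale.
- *The study would declare improved endothelial function when nothing changed.* Section 12.1.1 says the primary and secondary Efficacy Phase parameters "will be statistically tested using a 2-sided test at the 5% significance level"; FMD is neither. If a 95% t-interval were added to null trials of 30, it would lie wholly above zero in 4.9% to 6.7% of them over five assumed settings, against 2.5% nominal. That is inflated, but it is far from routine.

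**Conclusion.** The point holds as a low-severity flaw of scale. As fixed in the synopsis, Section 4.1.4 and Section 12.3.7, the mean per-patient percent change in FMD can drift upward with no true effect and can be strongly influenced by the lowest baselines. Under the stated assumptions a typical null trial of 30 reports from about +2% to +32%, while absolute change shows no drift. CIMT is not affected to any practical degree.

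The range rests on FMD being expressed as percent dilation and on assumed means and SDs, none of which the protocol gives. The consequence is a misleading descriptive estimate for an optional exploratory measure in a single-arm study. The primary test, the sample size and the Week 24 submission are untouched.

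**What to change.** In the synopsis exploratory endpoints, Section 4.1.4 and Section 12.3.7:

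- keep percent change from Baseline for CIMT;
- state the unit in which FMD is expressed;
- define the FMD endpoint as absolute change from Baseline (percentage points if FMD is percent dilation), summarised with a 95% CI.

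Keep every measured baseline. Under no effect, discarding baselines at or below 0.5 makes even the absolute change average −0.03 to −0.17 points over a set of assumed settings (mean 5 to 8, between-child SD 2 to 3, measurement SD 1.5 to 2). That is an artefact of the exclusion; with all baselines kept it is 0.00.

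The objective already allows this scale. The cost is a few words in three places, with no new data and no extra visits.
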